14.7 Registration of Clinical Trials and Disclosure of Results

The sponsor will register and/or disclose the existence of and the results of clinical trials as required by law.

16 APPENDICES

Appendix 1 Calculation of Glomerular Filtration Rate

Glomerular filtration rate (GFR) may be estimated based on commonly used and accepted formulae, ie

Cockcroft Gault formula

$$GFR = \frac{(140 - \text{age}) \times \text{weight} \times F_S}{\text{Serum Creatinine} \times 72}$$

Units: GFR [ml/min], age [years], weight [kg], serum creatinine [mg/dl], FS is a correction Factor for Sex: in males $F_S=1$, in females $F_S=0.85$

Modification of Diet in Renal Disease (MDRD) formula

$$GFR = 170 \times \text{Serum Creatinine}^{-0.999} \times \text{Age}^{-0.176} \times \text{BUN}^{-0.170} \times \text{Albumin}^{+0.318} \times F_S$$

Units: GFR [ml/min], age [years], serum creatinine [mg/dl], FS is a correction Factor for Sex: in males $F_S=1$, in females $F_S=0.762$

Variations of the MDRD formula

$$GFR = 186 \times \text{Serum Creatinine}^{-1.154} \times \text{Age}^{-0.203} \times F_S$$

Units: GFR [ml/min], age [years], serum creatinine [mg/dl], FS is a correction Factor for Sex: in males $F_S=1$, in females $F_S=0.742$

Appendix 2 New York Heart Association Criteria

Class	Subject Symptoms	Objective Assessment
I	No limitation of physical activity. Ordinary physical activity does not cause undue fatigue, palpitation, dyspnea (shortness of breath).	No objective evidence of cardiovascular disease. No symptoms and no limitation in ordinary physical activity.
II	Slight limitation of physical activity. Comfortable at rest. Ordinary physical activity results in fatigue, palpitation, dyspnea (shortness of breath).	Objective evidence of minimal cardiovascular disease. Mild symptoms and slight limitation during ordinary activity. Comfortable at rest.
III	Marked limitation of physical activity. Comfortable at rest. Less than ordinary activity causes fatigue, palpitation, or dyspnea.	Objective evidence of moderately severe cardiovascular disease. Marked limitation in activity due to symptoms, even during less-than-ordinary activity. Comfortable only at rest.
IV	Unable to carry on any physical activity without discomfort. Symptoms of heart failure at rest. If any physical activity is undertaken, discomfort increases.	Objective evidence of severe cardiovascular disease. Severe limitations. Experiences symptoms even while at rest.

Appendix 3 Corticosteroid Dose Equivalents

Steroid	Approximate Equivalent Dose	
Betamethasone	12 mg	Long-acting
Dexamethasone	15 mg	Long-acting
Methylprednisolone	80 mg	Intermediate-acting
Triamcinolone	80 mg	Intermediate-acting
Prednisone	100 mg	Intermediate-acting
Prednisolone	100 mg	Intermediate-acting

Appendix 4 Tumor Lysis Syndrome

Presence of TLS is not clearly defined by CTCAE. For this trial the Cairo-Bishop classification will be used to define the presence of TLS. Laboratory TLS (Table 35) will not be considered as presence of TLS in the absence of the specified clinical complications (Coiffier et al., 2008). Clinical TLS should be graded according to Table 36. Individual symptoms should be graded according to CTCAE.

As noted in Section 7.1, during Dose Escalation, Grade 4 TLS is considered a DLT. Refer to Sections 7.4.3.3 and 7.5.4 for relevant management and dose modification guidelines.

Table 35 Cairo-Bishop Definition of Laboratory Tumor Lysis Syndrome

Laboratory parameter	Value	Change from Baseline
Uric acid	$> 476 \mu\text{mol/L}$ or 8 mg/dL	25% increase
Potassium	$\geq 6.0 \text{ mmol/L}$ or 6 mg/L	25% increase
Phosphorus	$\geq 1.45 \text{ mmol/L}$	25% increase
Calcium	$\leq 1.75 \text{ mmol/L}$	25% increase

Note: 2 or more laboratory changes within 3 days before or 7 days after treatment with GEN3009. Based on (Coiffier et al., 2008).

Table 36 Cairo-Bishop Definition of Clinical Tumor Lysis Syndrome and Grading

Complication	Grade 1	Grade 2	Grade 3	Grade 4	Grade 5
Creatinine*†	$1.5 \times \text{ULN}$	$> 1.5\text{--}3.0 \times \text{ULN}$	$> 3.0\text{--}6.0 \times \text{ULN}$	$> 6.0 \times \text{ULN}$	Life-threatening (eg, arrhythmia associated with CHF, hypotension, syncope, shock)
Cardiac arrhythmia*	Intervention not indicated	Nonurgent medical intervention needed	Symptomatic and incompletely controlled medically or controlled with device (eg, defibrillator)		
Seizure*	None	One brief generalized seizure; seizure(s) well controlled by anticonvulsants or infrequent focal motor seizures not interfering with ADL	Seizure in which consciousness is altered; poorly controlled seizure disorder; with breakthrough generalized seizures despite medical intervention	Seizure of any kind which are prolonged, repetitive or difficult to control (eg, status epilepticus, intractable epilepsy)	Death

* Not directly or probably attributable to GEN3009

† If no institutional ULN is specified, ULN is defined as follows: female $105.6 \mu\text{mol/L}$, male $114.4 \mu\text{mol/L}$.

Based on (Coiffier et al., 2008).

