7.4.3.3 Tumor Lysis Syndrome (All Cohorts)

In cases of TLS, hold GEN3009 and/or GEN3013 (regardless of being monotherapy or combination therapy) until the TLS has resolved.

TLS should be reported as an AE, using the National Cancer Institute Common Terminology Criteria for Adverse Events (CTCAE) Version 5.0 grading, whereas clinical TLS should be reported as an AESI, using Cairo-Bishop grading (see [Appendix 4](#)).

Refer to Section [7.5.4](#) for prevention and management of TLS.

7.4.3.4 Immune Effector Cell-Associated Neurotoxicity Syndrome (GEN3009 + GEN3013 Combination Cohort)

ICANS has been reported with the use of GEN3013. To date, ICANS is not a known/identified risk with GEN3009. See [Table 27](#) for information on GEN3013 dose modification for ICANS. Refer to Section 7.5.3 for supportive care and Appendix 13 grading of ICANS.

Table 27 GEN3013 Dose Modification for ICANS (GEN3009 + GEN3013 Combination Cohort)

ICANS	
ASTCT Grade	Dose Modification
Grade 1 or 2	
Hold GEN3013 (and GEN3009 if given in combination) until resolution of ICANS to Grade 0 and treat the subject appropriately.
Grade 3 or 4	
Permanently discontinue administration of GEN3013 and treat the subject appropriately.

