10.2 Adverse Event Reporting

All AEs, whether serious or nonserious (see definition in section [10.1.2](#)), will be documented from the first dose of GEN3009 and/or GEN3013 (GEN3009 + GEN3013 cohort only) until 30 days after the last GEN3009 and 60 days after the last dose of GEN3013, subject withdrew consent, subject started new anti-cancer treatment, or the subject died, whichever comes first. Refer to the electronic case report form (eCRF) completion guidelines for additional information on reporting and stepwise guidance.

Medical conditions (signs, symptoms, and diagnoses) that occur after the ICF is signed and prior to the first GEN3009 and/or GEN3013 dose should only be reported as AEs if they were assessed by the investigator to be caused by a protocol-mandated procedure (ie, tumor biopsy and/or CT scan), including washout or discontinuation of prior medications.

The investigator will use the CTCAE Version 5.0 ([NCI, 2017](#)) to describe the intensity of AEs, except for TLS (refer to [Appendix 4](#)), CRS (refer to [Appendix 13](#)) and ICANS (refer to [Appendix 14](#)). Changes in intensity of an ongoing AE should be assessed at each visit or more frequent if deemed necessary and must be reported.

SAEs still ongoing after the safety follow-up visit(s) should be followed on a regular basis according to the investigator’s clinical judgment until the event has been resolved or until the investigator assesses it as chronic and all queries have been resolved. Only SAEs judged by the investigator as related to GEN3009 (all cohorts) and/or GEN3013 (the combination cohort only) should be reported after the safety follow-up visit.

The investigator must assess whether or not the event is related to the trial drug. The relationship is to be judged using the following terms:

- Related
- Not related

If the relationship changes over time, the last judgment by the investigator should be reported. Relatedness has to be assessed and reported from the first time the event is being reported.

A suspected adverse reaction is one in which there is a reasonable possibility that the trial drug caused the AE; this means there is evidence to suggest a causal relationship between the trial drug and the AE (ie, considered related).

Note:

- Final assessment of AEs must be performed by a medically qualified person, ie, a medical doctor.

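### Table 35 pairs a low calcium limit with a 25% increase, and the protocol sections and SAP disagree on the scale and AESI status of TLS: borderline classification and AE/AESI tabulation are affected, not the DLT grade

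*Protocol*

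**What the plan says.** **Laboratory definition (protocol Appendix 4, Table 35).** Each of four analytes has a value and a change from baseline. Uric acid, potassium and phosphorus have upper limits and a 25% increase. The calcium row reads "Calcium $\leq 1.75 \text{ mmol/L}$ 25% increase". The footnote sets the count and the window: "Note: 2 or more laboratory changes within 3 days before or 7 days after treatment with GEN3009". No and/or is stated between the two columns.

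**What counts as TLS (Appendix 4).** "For this trial the Cairo-Bishop classification will be used to define the presence of TLS". The next rule limits Table 35: "Laboratory TLS (Table 35) will not be considered as presence of TLS in the absence of the specified clinical complications". For severity, "Clinical TLS should be graded according to Table 36"; that table uses creatinine, cardiac arrhythmia and seizure.

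**Grading and reporting.** Section 7.4.3.3, which covers all cohorts, says "TLS should be reported as an AE, using the National Cancer Institute Common Terminology Criteria for Adverse Events (CTCAE) Version 5.0 grading", and in the same sentence that "clinical TLS should be reported as an AESI, using Cairo-Bishop grading". Section 10.2 uses CTCAE v5.0 "to describe the intensity of AEs, except for TLS" (and except CRS and ICANS), and sends the reader to Appendix 4 for TLS. SAP 11.1 grades AEs by CTCAE v5.0 or higher and makes no exception for TLS.

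**AESI list.** Section 10.3 names only infusion-related reactions (IRRs) for GEN3009 alone. Clinical TLS appears only under GEN3009 + GEN3013.

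**DLT.** Sections 7.2 and 7.3 both list Grade 4 TLS and refer to Appendix 4.

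**The concern.** The two calcium columns point in opposite directions, so the row cannot be applied as a coherent criterion whichever way the columns are combined. Calcium is one of four analytes and two changes are enough, so it can be the deciding one.

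A TLS event also carries different instructions depending on the section a site or programmer follows: CTCAE or Cairo-Bishop for the AE grade, and AESI or not in the monotherapy cohorts. At stake are the TLS grades and AESI counts in the safety tables and the deadline for entering a non-serious event. AESI frequency and severity are a primary endpoint in Dose Escalation and the safety run-in (Tables 17 and 19) and secondary in the monotherapy expansion (Table 18).

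**Working it through.** No sample size or stated figure depends on this point, so there is none to reproduce. The inputs are the 1.75 mmol/L limit and the 25% change in Table 35.

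**1. Calcium row, either column sufficient ('or').**
- A 25% fall from baseline B ends at 0.75 × B. It stays above the limit when 0.75 × B > 1.75, that is, B > 1.75/0.75 = 2.33 mmol/L.
- Example: 2.50 × 0.75 = 1.875 mmol/L. This is not at or below 1.75 and is not an increase, so it does not count.
- Example the other way: 2.00 × 1.25 = 2.50 mmol/L. This is a 25% increase, so it counts.
- At baselines of 2.33 or lower, a 25% fall already reaches the value limit, so nothing is missed there.

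**2. Calcium row, both columns required ('and').**
- The rise must end at 1.75 or lower: 1.25 × B ≤ 1.75, so B ≤ 1.75/1.25 = 1.40 mmol/L.
- Such a subject starts below the limit. No fall of any size qualifies, so the criterion is close to unusable.

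**3. From the calcium row to an outcome.** For the row to change whether a subject has TLS, two conditions must hold together:
- exactly one of the other three analytes qualifies, so that calcium decides whether there are two changes;
- a Table 36 complication is present, because laboratory TLS alone is not TLS here.

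This assumes that Table 35 is an entry condition for clinical TLS, which Appendix 4 implies but does not state. If a Table 36 complication sufficed by itself, the calcium row would not affect TLS at all. In neither case does calcium enter the Table 36 grade.

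**4. Grading scale, side by side.**

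| Place | TLS as AE | Clinical TLS as AESI | DLT |
|---|---|---|---|
| Protocol 7.4.3.3 | CTCAE v5.0 | Cairo-Bishop | not addressed |
| Protocol 10.2 | not CTCAE; see Appendix 4 | not addressed | not addressed |
| Appendix 4 | Cairo-Bishop (Table 36); individual symptoms by CTCAE | Table 36 | Grade 4 |
| Protocol 7.2, 7.3 | not addressed | not addressed | Grade 4, see Appendix 4 |
| SAP 11.1 | CTCAE v5.0 or higher | not addressed | not addressed |

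The conflict is in the AE column: 7.4.3.3 and SAP 11.1 against 10.2 and Appendix 4. The DLT column is consistent.

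**5. AESI status.** The contradictory wording covers the monotherapy cohorts: up to 90 in escalation plus 3 × 20 = 60 in expansion. These are subjects under the wording, not subjects with an event. Section 10.3 sets 24 hours for serious AESIs and 72 hours for entry of non-serious ones. Serious events are due within 24 hours as SAEs anyway (10.4.1), so the timing difference falls on non-serious clinical TLS.

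**6. How often an event might arise.** Section 2.1.4.2 reports clinical TLS in 1 of 68 subjects in the GEN3013 escalation. Assume that rate, or 5% as an upper illustration. The chance of at least one event in n subjects is 1 − (1 − p)^n.

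| n | p = 1/68 | p = 5% |
|---|---|---|
| 3 | 4.3% | 14.3% |
| 6 | 8.5% | 26.5% |
| 12 | 16.3% | 46.0% |

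These are events of any grade. The share in which calcium would be the deciding change is smaller, and the documents do not give it.

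**The case against.** The strongest reply is that little follows from the calcium row. A reader might infer that TLS is generally mis-classified, that dose-escalation decisions are at risk, or that treatment holds will be triggered wrongly. The documents do not support this:

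- Appendix 4 says laboratory TLS without clinical complications is not TLS, and the hold in 7.4.3.3 is for TLS.
- Both DLT lists point to Appendix 4, whose Table 36 does not use calcium.
- Non-hematologic events of Grade 3 or higher are already DLTs with listed exclusions, so a severe seizure or arrhythmia would generally count whatever its TLS label.
- Only the change column is at odds. The value limit remains usable on the 'or' reading, so it goes too far to call the whole criterion reversed.

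On the scale, 7.4.3.3 can be read as deliberate dual reporting: the AE on CTCAE, the AESI on Cairo-Bishop. That is a fair reading of the sentence, but it does not remove the conflict. Section 10.2 leaves no room for a CTCAE grade, and since only TLS with clinical complications counts as TLS, the same event would carry two grades. Neither document says which one enters the summaries.

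On AESI status, Section 10.3 is the list by regimen, 7.4.3.3 is a dose-modification section, and SAP 11.1.2 names only IRRs while allowing that others may be identified. A reader might infer that all 150 monotherapy subjects are affected. They are not: any TLS in them is still collected as an AE or SAE, and only AESI tabulation and the entry deadline can differ. For the 60 expansion subjects AESI frequency is not a primary endpoint. These limits stand; the inconsistencies remain.

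**Conclusion.** The point holds in a limited form. The calcium row contradicts itself in direction and fails on both readings of the table. It can mis-classify TLS only where calcium is the deciding second change and a Table 36 complication is present, and only if Table 35 is an entry condition for TLS. Such cases should be few if TLS is about as frequent as with GEN3013 alone, which is an assumption.

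The scale conflict (7.4.3.3 and SAP 11.1 against 10.2 and Appendix 4) and the AESI conflict (7.4.3.3 against 10.3) affect grades, AESI counts and entry timelines, including a primary endpoint in escalation and, for the scale conflict, in the run-in. No effect on the DLT grade or on an escalation decision is shown. These are wording errors that should be corrected; they do not call the design into question.

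**What to change.** - **Table 35:** reconcile the two calcium columns so that they agree in direction, and state for every row whether value or change suffices.
- **Scale:** reconcile 7.4.3.3, 10.2, Appendix 4 and SAP 11.1, naming the scale used for TLS as an AE, as an AESI and as a DLT. If two grades per event are intended, say so in 10.2 and say which one the SAP tabulates. The SAP is written against protocol version 4.0, so it needs updating to the current amendment in any case.
- **AESI:** make 7.4.3.3 and 10.3 agree on whether clinical TLS is an AESI in the monotherapy cohorts.
- **Cross-reference:** Appendix 4 cites Section 7.1 and Dose Escalation only for the DLT rule. Section 7.1 is an empty heading, and the rule sits in 7.2 and 7.3.

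Which clinical rule and which scale to adopt is for the sponsor. The cost is wording in the protocol and SAP; TLS sampling is already scheduled. The possible downside is a few more subjects classified with laboratory TLS.

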Appendix 5 Ann Arbor Staging

Stage	Area of Involvement
I	Single lymph node or lymph node region
II	Two or more lymph node regions on same side of diaphragm
III	Lymph node regions on both sides of the diaphragm are affected
IV	Disease is wide spread, including multiple involvement at 1 or more extranodal sites (beyond the lymph node, spleen, tonsils and Waldeyer's ring), such as the bone marrow, liver or pleura
A	Without disease symptoms
B	With symptoms like night sweats, weight loss > 10% over 6 months, fever without infection
E	Extranodal disease

Appendix 6 Rai and Binet Staging

Rai Staging System

Low-risk disease	Lymphocytosis with leukemia cells in the blood and/or marrow
Intermediate-risk disease	Peripheral blood lymphocytosis, enlarged lymph nodes in any site, and splenomegaly and/or hepatomegaly (lymph nodes being palpable or not)
High-risk disease	Disease-related anemia (as defined by a Hb level <1 g/dL) or thrombocytopenia (as defined by a platelet count of <100 × 10 ⁹ /L)

[Hallek et al., 2018](#)

Binet Staging System

Stage	
A	Hb ≥10 g/dL and platelets ≥100×10 ⁹ /L and up to 2 areas involved
B	Hb ≥10 g/dL and platelets ≥100×10 ⁹ /L and 3 or more lymphoid areas involved
C	Hb <10 g/dL and/or a platelet count <100 × 10 ⁹ /L)

Areas of involvement considered for staging include:

1. Head and neck, including the Waldeyer ring (this counts as 1 area, even if ≥1 group of nodes is enlarged)
2. Axillae (involvement of both axillae counts as just 1 area)
3. Groins, including superficial femorals (involvement of both groins counts as just 1 area)
4. Palpable spleen
5. Palpable liver (clinically enlarged)

[Hallek et al., 2018](#)

Appendix 7 Response Criteria for B-cell NHL by CT Scan

Response	Lymph Nodes	Non-Measurable Lesion	Organ Enlargement	New Lesions	Bone Marrow
CR	Target nodes/nodal masses regression ≤ 1.5 cm in longest diameter	Absent	Regress to normal	None	Normal by morphology; if indeterminate, IHC negative
PR	$\geq 50\%$ decrease in SPD of up to 6 target measurable nodes and extranodal sites	Absent/normal, regressed, but no increase	Spleen regressed $>50\%$ in length beyond normal	None	Not applicable
No response or SD	$<50\%$ decrease in SPD of up to 6 target measurable nodes and extranodal sites	No increase consistent with progression	No increase consistent with progression	None	Not applicable
PD	>1.5 cm and increase by $\geq 50\%$ from nadir and increase from nadir 
• 0.5 cm for lesions ≤ 2 cm• 1.0 cm for lesions >2 cm	New or clear progression of pre-existing lesions	Spleen length increase of $>50\%$ from baseline or if no prior splenomegaly, must increase by at least 2 cm from baseline	Regrowth of previously resolved lesions; new nodes >1.5 cm in any axis; new extranodal site >1.0 cm in any axis; assessable disease of any size unequivocally attributable to lymphoma	New or recurrent involvement

(Cheson et al., 2014)

Appendix 8 Response Criteria for CLL

Group and Parameters	Complete Remission (CR)**	Partial Remission (PR)**	Progressive Disease (PD)	Stable Disease (SD)
Group A – assess the lymphoid tumor load and constitutional symptoms				
Lymph nodes	None ≥ 1.5 cm	Decrease $\geq 50\%$ from baseline*	Increase $\geq 50\%$ from baseline or from response	Change of -49% to +49%
Liver and/or spleen size†	Liver size normal; spleen size < 13 cm	Decrease $\geq 50\%$ from baseline	Increase $\geq 50\%$ from baseline or from response	Change of -49% to +49%
Constitutional symptoms	None	Any	Any	Any
Circulating lymphocyte count	$< 4 \times 10^9/L$	Decrease $\geq 50\%$ from baseline	Increase $\geq 50\%$ from baseline	Change of -49% to +49%
Group B – assess the hematopoietic system				
Platelet count	$\geq 100 \times 10^9/L (\geq 00,000 \mu L)$	$\geq 100 \times 10^9/L (\geq 100,000 \mu L)$ or increase $\geq 50\%$ over baseline	Decrease $\geq 50\%$ from baseline secondary to CLL	Change of -49% to +49%
Hemoglobin	$\geq 11.0 \text{ g/dL}$ (untransfused and without erythropoietin)	$\geq 11.0 \text{ g/dL}$ or increase of $\geq 50\%$ over baseline	Decrease of $\geq 2.0 \text{ g/dL}$ from baseline, secondary to CLL	Increase $< 11.0 \text{ g/dL}$ or $< 50\%$ over baseline or decrease $< 2.0 \text{ g/dL}$
Bone marrow	Normocellular, no CLL cells, no B-lymphoid nodules	Presence of CLL cells or B-lymphoid nodules, or not done	Increase of CLL cells by $\geq 50\%$ on successive biopsies	No change in marrow infiltration

*Sum of the products of 6 or fewer lymph nodes (as evaluated by CT scans and physical examination in clinical trials or by physical examination in general practice).

†Spleen size is considered normal if < 13 cm. There is not firmly established international consensus of the size of a normal liver; therefore, liver size should be evaluated by imaging and manual palpation and recorded.

**CR, (all of the criteria have to be met); PD (at least 1 of the criteria of group A or group B has to be met); PR (for a PR, at least 2 of the parameters of group A and 1 parameter of group B need to improve if previously abnormal; if only 1 parameter of both groups A and B is abnormal before therapy, only 1 needs to improve); SD (all of the criteria have to be met; constitutional symptoms alone do not define PD).

Nodular partial remission is defined as a bone marrow biopsy showing residual nodules or suspicious lymphocytic infiltrates in subjects who are in remission; which often indicates a residual disease.

(Hallek et al., 2018)

Appendix 9 PET Positivity Evaluation

Evaluation of PET positivity should be performed according to the 5-point scale (5-PS) adopted from the Deauville criteria described in ([Barrington et al., 2014](#)).

The 5-PS was intended as a simple, reproducible scoring method, with the flexibility to change the threshold between good or poor response according to the clinical context and/or treatment strategy. For example, a lower level of FDG uptake might be preferred to define a so-called negative result in a clinical trial exploring de-escalation to avoid undertreatment. A higher level of uptake might be preferred to define a so-called positive result in a trial exploring escalation to avoid overtreatment. The 5-PS has been validated for use at interim and the end of treatment.

The 5-PS scores the most intense uptake in a site of initial disease, if present, as follows:

1 no uptake

2 uptake \leq mediastinum

3 uptake $>$ mediastinum

4 uptake moderately higher than liver

5 uptake markedly higher than liver and/or new lesions

X new areas of uptake unlikely to be related to lymphoma

